8. Instructions for measuring orthostatic vital signs will be provided to subjects prior to the follow-up visit. If they have a means for measuring blood pressure they will take these measurements and report them at their visit. A notation will be added to the dataset indicating that these were measured by the subject since these measures may not be consistent with those that would have been obtained at the clinical research center.
9. The research coordinator will call subjects weekly to inquire about adverse events beginning the week after the remote visit has taken place as a safeguard given the inability to conduct a physical and neurological exam and to have the research nurse measure orthostatic vital signs. Weekly calls will continue until the next in-person visit has taken place.
10. If restrictions due to COVID-19 are lifted within 4 weeks of the remote visit, an in-person visit will be scheduled and the physical examination, neurological examination, MDS-UPDRS III, Hoehn and Yahr Staging, and orthostatic vital signs will be taken during this visit.

11. Subjects will be sent a new consent form and have the changes reviewed by phone. They will be asked to sign the consent form and return via email or paper mail. Once received, the form will be signed by the study team member obtaining consent and sent back to the subject.

The following data will be collected at follow-up visits at weeks 8, 24, 40 and 52.

Table 3. Follow-up data at weeks 8, 24, 40 and 52

Data	Detail
General health status	Physical examination findings ^a Neurological examination findings ^a Concomitant medications Height, weight, orthostatic vital signs ^b
PD motor symptoms	MDS-UPDRS part III ^c

The following modifications will be made for visits taking place remotely, as will be required during the COVID-19 pandemic:

^aThese measurements will not take place for visits taking place remotely

^bThese measures will be taken by the subject, if they have the capacity to do so, for visits taking place remotely

^cA modified version of this measure will be administered for visits taking place remotely

Orthostatic vital signs will be obtained by measuring vital signs after 5 minutes supine and after 2 minutes standing.

The following data will be collected at the follow-up visit at week 56.

Table 4. Follow-up data at week 56

Data	Detail

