General health status	Physical examination findings ^a Neurological examination findings ^a Concomitant medications Height, weight, orthostatic vital signs ^b
PD symptom burden	MDS-UPDRS score (parts I, II ^d , III ^c , IV)
Health-related quality of life	Parkinson's Disease Questionnaire-39 (PDQ-39) ^d
PD stage	Modified Hoehn & Yahr staging
Cognitive status	Montreal Cognitive Assessment (MoCA) ^c
Emotional status	Geriatric Depression Scale – short form (GDS-15) ^d

The following modifications will be made for visits taking place remotely, as will be required during the COVID-19 pandemic:

^aThese measurements will not take place for visits taking place remotely

^bThese measures will be taken by the subject, if they have the capacity to do so, for visits taking place remotely

^cA modified version of this measure (mUPDRS) will be administered for visits taking place remotely

^dThese measures will be administered online via RedCap for visits taking place remotely

In a similar manner to the baseline visit, if subjects are on parkinsonian medication, assessment of motor symptoms (UPDRS-part III) and PD stage (Modified Hoehn & Yahr) at week 56 will

be performed in the practically defined “off” and “on” medication states. Assessment of cognitive status will be performed in the practically defined “off” medication state.

Orthostatic vital signs will be obtained by measuring vital signs after 5 minutes supine and after 2 minutes standing.

D5. f. Follow-up phone calls

After the screening/baseline visit, the study coordinator will follow-up with the patient by phone at weeks 4, 16, 32, and 48. During the phone calls, the study coordinator will ask the subject about any adverse effects from the study drug. The subject will be reminded to call the investigator to report any adverse events. Subjects will also be asked if they have been compliant with taking the study medication as instructed.

After the last visit, the study coordinator will follow-up with the subject one last time by phone. The purpose of this phone call will be to ascertain the subject’s medical status, to determine whether any ongoing adverse events present at the last clinic visit have resolved, and to inquire if any other adverse events have occurred since the last visit.

D5. g. Early Termination

Subjects will have the right to voluntarily discontinue study treatment and study visits at any time and for any reason.

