Occurrence of severe adverse events attributed to study participation will result in immediate withdrawal from the study and termination of study medication. Subjects who are not compliant with taking the study medication as instructed will also be withdrawn early from the study.

Subjects who discontinue the study drug prior to week 52 will be seen for a final visit as soon as possible after study drug discontinuation.

Table 5. Study Overview

Assessments	Screening visit	Baseline visit (Week 0)	Phone contact (Weeks 4, 16, 32, 48)	Follow-up (Weeks 8, 24, 40, 52)	Final visit/ Early termination (Week 56)	Phone contact (Week 58)
Informed Consent	x					
Inclusion/Exclusion Criteria	x					

Medical history		x		x	x	
Physical examination		x		x ^a	x ^a	
Neurological examination		x		x ^a	x ^a	
Height, weight, orthostatic vital signs		x		x ^b	x ^b	
MDS-UPDRS, parts I, II, IV		x			x ^c	
MDS-UPDRS, part III (obtained in “off” and “on” states)		x			x ^d	
MDS-UPDRS, part III (obtained in “on” state)				x ^d		
Modified Hoehn & Yahr (obtained in “off” and “on” states)		x			x	
PDQ-39		x			x ^c	
Pregnancy test (if needed)	x					
GDS-15		x			x ^c	
MoCA (obtained in “off” state)		x			x ^d	
Adverse event review			x	x	x	x
Randomization		x				
Record concomitant medications		x	x	x	x	x
Study drug dispensation		x		x ^e		
Tablet count				x		

Blood draw		X				
------------	--	---	--	--	--	--

The following modifications will be made for visits taking place remotely, as will be required during the COVID-19 pandemic:

^aThese measurements will not take place for visits taking place remotely

^bThese measures will be taken by the subject, if they have the capacity to do so, for visits taking place remotely

^cThese measures will be administered online via RedCap for visits taking place remotely

^dA modified version of this assessment will be administered for visits taking place remotely

^e Does not include week 52; for visits taking place remotely, the study medication will be mailed to the subject prior to the visit.

Subjects can withdraw from the study at any time.

D6. Study Drug

Preparation

H_2 can be dissolved in water at atmospheric pressure up to a saturating concentration of 0.8 mM (1.6 ppm), and tissue protection has been demonstrated in a number of rat models using either infusion of H_2 -enhanced IV fluids or ad lib access to H_2 -enriched drinking water.

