1. **Motor Symptoms:** To investigate the effect of H₂-enriched water on the progression of motor symptoms in PD patients. Progression of motor symptoms will be assessed by change in the motor subscale of the MDS-Unified Parkinson's Disease Rating Scale (MDS-UPDRS-III) from baseline to week 56. This will be assessed in the “off” state.
2. **Quality of life:** To investigate the effect of H₂-enriched water on health-related quality of life in PD patients. Health-related quality of life will be assessed by change in the PDQ-39 from baseline to week 56.
3. **Cognitive Function:** To investigate the effect of H₂-enriched water on the progression of cognitive decline in PD patients. Cognitive function will be assessed using the Montreal Cognitive Assessment (MoCA) scale at baseline and week 56. This will be assessed in the “off” state.
4. **PD Symptom Burden:** To investigate the effect of H₂-enriched water on the progression of symptom burden in PD patients. Progression of symptom burden will be assessed by change in the Total MDS-UPDRS from baseline to week 56.

D8. Enrollment Failure

Subject enrollment will be examined continuously. Our goal is to enroll the targeted 70 subjects within 3 years of enrolling the first subject. If enrollment rate by the end of 18 months is not on

track towards approaching this goal, and no prospects for enhancing enrollment are on the horizon (for example, through partnership with another medical center or network), we will terminate the study and analyze outcomes based upon subjects enrolled at that point. If enrollment is proceeding well, but a reasonable extension of time is needed to complete enrollment of the targeted 70 subjects, we will submit an appropriate amendment request to the IRB prior to the end of the 3 year time frame.

E. STATISTICS

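### Subjects with severe attributed adverse events and non-compliant subjects are withdrawn from the study, not only from study drug, so they have no week-56 value and SAE observation ends early

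*Combined protocol and SAP*

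**What the plan says.** All references are to the combined protocol and SAP.

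- **D5.g, Early Termination.** For one group, "Occurrence of severe adverse events attributed to study participation will result in immediate withdrawal from the study", and study medication is stopped as well. For the other, "Subjects who are not compliant with taking the study medication as instructed will also be withdrawn early from the study". No compliance threshold is given, and nothing is said separately about study drug for this group. Voluntary discontinuation is a separate sentence in the same section.
- **D5.g, stopping before week 52.** Subjects who stop drug before week 52 "will be seen for a final visit as soon as possible after study drug discontinuation". No later visit is scheduled for them.
- **Table 5.** This visit shares a column with the week-56 visit; the heading reads "Final visit/ Early termination (Week 56" (closing bracket omitted). The column schedules the whole outcome battery.
- **D5.f.** "After the last visit, the study coordinator will follow-up with the subject one last time by phone". Table 5 puts this call at week 58 for completers.
- **D7b.** The secondary outcomes are tied to week 56. For example, "Progression of symptom burden will be assessed by change in the Total MDS-UPDRS from baseline to week 56".
- **Section E.** Safety is compared by a log-rank test of time to first SAE. The increase from 60 to 70 subjects is explained by voluntary drop-out alone.
- **H 2.** Missing data are to be obtained where possible. No method for handling them is given.

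**The concern.** A randomised comparison is protected by following everyone who was randomised. Here the protocol itself removes subjects for reasons that arise after randomisation and may depend on treatment: an adverse event attributed to the study, or failure to take the tablets.

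Two analyses are exposed. In the log-rank test, a subject removed without a prior SAE is censored at about the closing call. The test assumes that censoring is unrelated to later SAE risk, and that is doubtful when the reason is an attributed adverse event or poor adherence. For the secondary outcomes, the week-56 value is missing for the same reasons. Unlike a missing analysis rule, this cannot be repaired at the analysis stage, because the data will not have been collected.

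**Working it through.** **1. The plan's own sample size.** Inputs are the pilot UPDRS-III changes in section C: −5.8 ± 7.2 against 2.3 ± 8.5.

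- Difference = 2.3 − (−5.8) = 8.1.
- SD = √((7.2² + 8.5²)/2) = 7.88.
- Two-sample t test, two-sided alpha 0.01: 30 per arm gives 90.2% power. The plan's total of 60 is reproduced.

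Section E prints other figures (difference 9.8; SDs 8.4 and 9.2, giving 8.81). These give 94.6% at 30 per arm. Both sets are used below.

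**2. SAE observation lost.** Planned observation is 70 × 58 = 4060 person-weeks. Assume the final visit falls at the stopping week t and the closing call 2 weeks later, as the gap from week 56 to week 58 in Table 5 suggests. Each stopper then loses 58 − (t + 2) weeks: 48 at week 8, 32 at week 24, 16 at week 40.

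| Stoppers (assumed) | All at week 8 | All at week 24 | All at week 40 |
|---|---|---|---|
| 4 | 192 (4.7%) | 128 (3.2%) | 64 (1.6%) |
| 10 | 480 (11.8%) | 320 (7.9%) | 160 (3.9%) |
| 20 | 960 (23.6%) | 640 (15.8%) | 320 (7.9%) |

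These are upper bounds. A stopper who has already had an SAE has contributed the event and loses nothing for this endpoint. The percentages measure lost observation, not bias.

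**3. Power if stoppers are followed or lost.** Assume stoppers are split evenly between arms and that active-arm stoppers take the placebo mean and SD. With a fraction f of the active arm still on treatment:

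- diluted difference = f × 8.1
- active-arm variance = f × 7.2² + (1 − f) × 8.5² + f(1 − f) × 8.1²
- mixture SD = √((active-arm variance + 8.5²)/2)

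For 10 stoppers, f = 30/35. The difference is 6.94, the active-arm variance is 62.8, and the mixture SD is √((62.8 + 72.25)/2) = 8.22.

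| Stoppers | f | Difference | Mixture SD | Power, all 70 followed | Power, stoppers lost |
|---|---|---|---|---|---|
| 4 | 33/35 | 7.64 | 8.03 | 90.4% | 93.2% (33 per arm) |
| 10 | 30/35 | 6.94 | 8.22 | 80.8% | 90.2% (30 per arm) |
| 20 | 25/35 | 5.79 | 8.47 | 58.5% | 82.5% (25 per arm) |

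With the section E figures and 10 stoppers, the difference is 9.8 × 30/35 = 8.4 and the mixture SD is 9.19. Power is 87.6% if followed and 94.6% if lost. The two columns answer different questions, so the higher figure is not evidence that losing the subjects is better.

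**The case against.** **The outcome data are not absent.** A reader might infer that withdrawn subjects leave with no outcome data. Table 5 does not support that: the full battery is scheduled when they stop, and earlier visits collect MDS-UPDRS part III in the on state. What is missing is a measurement at week 56. A reader might also infer from the shared column that early values will be analysed as week-56 values. The layout leaves that open, but nothing in the documents says so.

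**Only two groups are explicitly withdrawn.** For other drug stops before week 52, the end of follow-up is implied by the prompt final visit and the lack of any later schedule. A late stopper's final visit could also fall close to week 56.

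**Some adverse events already count.** If the severe event is also serious, time to first SAE is already observed. Adverse-event-driven stopping is also information for the tolerability outcome. Both points stand and narrow the concern. Severe and serious are different terms, however, and a non-compliant subject need have had no event.

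**Extra calls may exist.** After a remote visit, "Weekly calls will continue until the next in-person visit has taken place". It is unclear whether this covers a remote final visit, and it is a temporary COVID-19 provision.

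**An on-treatment question may be intended.** Ending observation soon after drug would suit it, and following everyone lowers power. The plan does not state that question. Safety is the primary objective, and efficacy is called exploratory.

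**The rate is unknown.** This stands. The 10 extra subjects are described for voluntary drop-outs, so they do not estimate these withdrawals. The pilot reported no adverse events or drop-outs among 9 active patients, which is too few to set a rate.

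**Conclusion.** The point holds as a design weakness that should be corrected. Followed as written, D5.g removes randomised subjects on grounds that may be related to treatment. It leaves them without a week-56 value and ends SAE observation early for those with no prior SAE.

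That the rule does this is clear from the text; how much it matters is not. The range of 1.6% to 23.6% rests wholly on assumed numbers and timing of stoppers and is a ceiling for each case. It would be tempting to conclude that the safety or efficacy comparison is biased towards the active arm. The documents do not support that: they give neither the rate of these withdrawals nor their split by arm, so informative censoring is possible but its direction is unknown.

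**What to change.** **(a) Amend D5.g.** Any subject in these two groups, and any other subject who stops study drug, stays on the existing visits and calls through week 56 and the week-58 call unless consent for follow-up is withdrawn, and is analysed as randomised. On-treatment analyses may be added as supportive. The rules on study drug are outside this point. The sponsor should, however, reconcile D5.g so that it says separately, for non-compliant subjects, what applies to study drug and what applies to follow-up.

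**(b) Amend Table 5.** Give early termination its own column and state that its values are not used as week-56 values.

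**Cost.** This is a short amendment. A subject who stops at week 8 adds up to four visits (weeks 24, 40, 52, 56) and four calls (weeks 16, 32, 48, 58), in a trial launched on the investigators' own funds. The efficacy contrast is diluted to the extent shown in the power table, which is modest with few stoppers and large with 20. The sponsor should accept that trade-off knowingly.

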A recent small pilot randomized double-blind placebo-controlled trial involving a total of 17 patients with idiopathic PD treated with levodopa (Hoehn & Yahr stages I – IV; average disease duration of 6.5 and 7.2 years for active treatment and placebo arms, respectively) demonstrated that drinking 1000 mL/day of H₂-enriched water for a total of 48 weeks was safe and well-tolerated in this patient cohort, with no adverse events reported. Notably, patients in the active treatment arm demonstrated significant improvement in total scores on the Unified Parkinson's Disease Rating Scale (UPDRS) when compared to placebo (-5.7 ± 8.4 vs. 4.1 ± 9.2 for active treatment vs. placebo, respectively). Changes in the motor subscale of the UPDRS (UPDRS-III), a secondary outcome measure, trended towards significance (-5.8 ± 7.2 vs. 2.3 ± 8.5 for active treatment vs. placebo, respectively; p = 0.074)¹³. Despite the promising results from this small pilot study, its design is inherently unable to differentiate between disease-modifying and symptomatic effect. Additionally, the recruited patients were relatively advanced in the course of their disease, when the pool of existing dopaminergic neurons was likely quite low, and the disease-modifying potential for the treatment therefore diminished.

A follow-up randomized double-blind placebo-controlled multi-center trial to assess the efficacy of H₂ in a larger sample of PD patients, including those not on levodopa, is currently underway.¹⁴ Several aspects of the design of this ongoing study are concerning, however. Enrolled patients had an average disease duration of 6.8 ± 4.5 years at time of study onset, indicating that many of the study participants have a small pool of salvageable dopaminergic neurons. In addition, the H₂-enriched water provided to patients in this study is distributed weekly in plastic bottles, through which H₂ is able to rapidly diffuse over a period of minutes to hours. The H₂ concentration at the time of consumption is thus unclear.

Here, we propose a double-blind placebo-controlled study to investigate the safety and tolerability, and to explore the efficacy, of H₂-enriched water in a population of early-stage PD

patients. We seek to enroll a total of 70 patients with early-stage PD, and will make use of a practical method our department has considerable experience with in order to generate H₂-enriched water.

D. RESEARCH DESIGN AND METHODS

D1. Rationale/Overview

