The primary objective of this study will be to assess the safety and tolerability of H₂-enriched water in patients with PD. Safety will be assessed by comparing time to first SAE by log-rank tests. As noted above, safety is defined as the absence of serious adverse events (SAEs) warranting termination of the treatment arm or the trial, as determined by the Data and Safety Monitor. Tolerability will be defined as the extent to which the treatment group can continue without prolonged treatment suspension (>24 consecutive days or >36 cumulative days) due to adverse events (AEs), as assessed 24 and 52 weeks after receiving the study drug. The study is reasonably powered to detect the emergence of an SAE; of note, there were no adverse events or drop-outs in the active treatment arm of a prior pilot study including 9 patients on active treatment with H₂-enriched water¹³.

We also plan to perform an exploratory analysis looking for evidence of benefit against disease progression in PD using the secondary outcome measures described above (see D7b). In order to obtain meaningful results towards this end, we have therefore powered the study to detect a superiority of treatment with H₂-enriched water compared to placebo in slowing PD disease progression. A prior pilot study demonstrated changes in the motor subscale of the UPDRS (UPDRS-III) that trended towards significance when comparing active treatment with H₂-enriched water to placebo (-5.7 ± 8.4 vs. 4.1 ± 9.2 for active treatment vs. placebo, respectively). Power calculation using this data suggests that a sample size of 60 will be sufficient to detect a between-group difference with a 2-sided $\alpha = 0.01$ and power = 90%. We plan on a sample size of 70 to account for drop-outs who voluntarily discontinue study treatment and study visits, and are therefore lost to follow-up.

F. FUNDING STATUS, DETAILS

This is an investigator-initiated study that will be funded at launch from the investigators' own uncommitted research funds, possibly with assistance from the Department of Neurology. The investigators may seek outside funding if interim results are encouraging.

G. HUMAN SUBJECTS RESEARCH PROTECTION FROM RISK

G 1. Risk to Subjects

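### Section E gives total-UPDRS pilot figures as UPDRS-III power inputs; the stated 60 matches the UPDRS-III figures in Section C, and power for slowing progression is not shown

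*Combined protocol and SAP*

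**What the plan says.** Section E (Statistics) calls the efficacy work an "exploratory analysis looking for evidence of benefit against disease progression in PD". It nevertheless says the study has been powered to show superiority "compared to placebo in slowing PD disease progression". As the basis it cites a pilot that showed "changes in the motor subscale of the UPDRS (UPDRS-III) that trended towards significance", prints -5.7 ± 8.4 (active) vs 4.1 ± 9.2 (placebo), and continues: "Power calculation using this data suggests that a sample size of 60 will be sufficient". The settings are two-sided alpha 0.01 and 90% power, and 60 is raised to 70 for drop-outs. No test is named.

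Section C (Preliminary Studies) describes the same pilot differently. There the four numbers belong to the total scale, as a "significant improvement in total scores on the Unified" scale, "when compared to placebo (-5.7 ± 8.4 vs. 4.1 ± 9.2 for active treatment vs. placebo, respectively". The UPDRS-III result is given separately, with a negative active-arm mean, as "5.8 ± 7.2 vs. 2.3 ± 8.5 for active treatment vs. placebo, respectively; p = 0.074", and it is this result that Section C calls a trend. Section C adds that for the pilot "its design is inherently unable to differentiate between disease-modifying and symptomatic effect".

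The motor endpoint of this trial (Section D7b) is the change in off-state MDS-UPDRS-III from baseline to week 56.

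**The concern.** Both sections cite the same pilot, so the four numbers cannot be both total-UPDRS and UPDRS-III changes. They are the stated inputs to the only quantitative justification of the sample size. As written, a reader cannot tell which endpoint and which figures produced 60.

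The second issue is what the 90% refers to. The power was computed for the pilot's between-group difference, most of which is improvement in the active arm. Section E presents it as power to show slowing. Section B says the efficacy results are meant to inform whether and how H₂ goes to phase 3. If a null result were read against an unsupported 90% figure, it could be taken as evidence against slowing that the trial was never sized to provide.

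**Working it through.** **Inputs.** Two-sided alpha 0.01, power 90% and the printed means and SDs are from Section E. The 1:1 allocation is from Section D4, and the UPDRS-III means and SDs are from Section C.

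**Method.** Two-sample t-test (noncentral t), with SD = √((SD₁² + SD₂²)/2). The noncentrality at n per arm is (difference/SD)/√(2/n).

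**Reproducing the stated 60**

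- Figures printed in Section E: difference 4.1 − (−5.7) = 9.8; SD = √((8.4² + 9.2²)/2) = 8.81. Required n = 25.76, so 26 per arm, **N = 52**. Power at 30 per arm is 94.6%. The normal approximation gives 50; using the larger SD of 9.2 in both arms gives 56.
- UPDRS-III figures in Section C: difference 2.3 − (−5.8) = 8.1; SD = √((7.2² + 8.5²)/2) = 7.88. Required n = 29.85, so 30 per arm, **N = 60**. Power at 30 per arm is 90.2%; at 29 per arm it is 88.9%. The normal approximation gives 58.
- Mixed pairings: 9.8 with SDs 7.2/8.5 gives 42; 8.1 with SDs 8.4/9.2 gives 74.

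Of the four pairings, only the UPDRS-III pair returns 60 under the stated alpha and power with a t-test.

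**Is a slip proven?** No. A rank test sized at its lower-bound efficiency of 0.864 would take the printed figures to 25.76/0.864 = 29.8, so 30 per arm, or 60 (62 if 26 is inflated after rounding). At the normal-theory efficiency of 0.955, 25.76/0.955 = 27.0, so 27 per arm, or 54.

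A check on the labels points the same way without settling it. It assumes 9 active patients (Section E) and 17 − 9 = 8 placebo patients. A t-test on the -5.7 vs 4.1 set then gives p = 0.036, in line with Section C calling it significant. The UPDRS-III set gives p = 0.050, not the 0.074 in Section C, so the pilot may have used a different test.

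**What the difference consists of**

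| | UPDRS-III (Section C) | Total UPDRS (Section C) |
|---|---|---|
| Improvement from baseline on active | 5.8 | 5.7 |
| Worsening on placebo | 2.3 | 4.1 |
| Difference | 8.1 | 9.8 |

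If H₂ only halted progression completely, the expected difference would be the placebo worsening alone. At 30 per arm the noncentrality is then (2.3/7.88)/√(2/30) = 1.13 on UPDRS-III, power about 7%. On total UPDRS it is (4.1/8.81)/√(2/30) = 1.80, power about 20%. These powers are illustrative. They borrow the pilot's placebo change, because the plan gives no expected progression for patients diagnosed within 3 years.

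**Sensitivity to SD.** With an 8.1-point difference and the pilot's larger arm SD of 8.5, power at 30 per arm is 84%.

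**Interval width at 30 per arm, SD 7.88.** The 99% half-width is 2.663 × 7.88 × √(2/30) = 5.4 points. The 95% half-width is 2.002 × 7.88 × √(2/30) = 4.1 points.

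**The case against.** The strongest reply is that nothing about the trial changes. Section E says 60 is sufficient, and at the pilot SDs that is true on both sets: 52 are needed on one and 60 on the other. The analysis is secondary and exploratory, and the primary outcomes are safety and tolerability. All of this stands. A reader might infer that the mislabelling leaves the trial short of patients; the figures do not support that.

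A reader might also infer that the calculation certainly used the UPDRS-III figures and that only the printed numbers are wrong. The arithmetic favours this, but with no test named and the pilot report not in the documents it remains an inference.

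On slowing, Section D7b defines progression as change on the MDS-UPDRS-III, so a between-group difference in change is the protocol's own measure. The endpoint is also taken off medication at week 56, after 52 weeks of therapy (Section D6). That helps the interpretation of an observed difference, but it does not turn 8.1 or 9.8 points into a plausible slowing effect.

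Finally, the pilot SD comes from 17 levodopa-treated patients with mean disease duration of 6.5 and 7.2 years by arm, scored on the UPDRS. It is tempting to call its use here an error. The documents give no SD for early PD on the MDS-UPDRS-III, and Section C argues that advanced disease reduced the scope for disease modification in the pilot, which could favour a larger effect here. Carrying the SD over is an assumption that needs a caveat, not a mistake.

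**Conclusion.** Sections C and E contradict each other on which endpoint the four numbers describe, and the stated 60 does not follow from the printed figures under a t-test (52, with 94.6% power at 30 per arm). It follows exactly from Section C's UPDRS-III figures (60, 90.2%). The likely cause is that the wrong row of pilot results was copied into Section E.

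The claim of power for slowing is unsupported on either set. About 5.7 to 5.8 points of the assumed difference are improvement below baseline, in a pilot that the protocol itself says cannot isolate disease modification.

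This should be fixed, but it is a correction to the stated justification and not a reason to enlarge the trial. The conclusion assumes a two-sample t-test with equal arms and pilot SDs that carry over. The 7% and 20% also assume that the pilot's placebo change carries over.

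**What to change.** In Section E:

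1. Check Sections C and E against the pilot report, correct whichever is wrong, and print the endpoint, means, SDs and test actually used.
2. Restate the power for that difference. If the endpoint was UPDRS-III, suitable wording is: *60 completers give about 90% power at two-sided alpha 0.01 (t-test) for a between-group difference of about 8.1 points, assuming the pilot SD of about 7.9 carries over to off-state MDS-UPDRS-III in early PD.*
3. Delete the statement that the study is powered for slowing, or justify the difference with an expected off-state progression in this population.
4. Add one caveat: the SD comes from 17 more advanced, levodopa-treated patients scored on the UPDRS, and power for 8.1 points falls to 84% at the pilot's larger arm SD of 8.5.
5. Report the efficacy result with a confidence interval that matches alpha 0.01 (99%, about ±5.4 points at SD 7.9), or explain why a 95% interval (about ±4.1) is used. Otherwise a difference between 4.1 and 5.4 points would be null at 0.01 while the 95% interval excludes zero.

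The cost is a few sentences and up to four numbers. No patients, visits, endpoints or procedures change. The only downside is a less favourable stated power property.
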